## 14.4 Sample size calculation

Studies comparing active eczema treatments with placebo have generally found large effect sizes ( $>0.7$ ). There are no data available on the likely effect size identified by POEM. In a study of children with 'moderate to severe eczema' the median baseline POEM score was 13 (out of 28). Assuming a clinically important difference of 3 on the POEM score and a common standard deviation of 7, we estimate a meaningful effect size of 0.429. The main analysis will be a comparison of each active treatment with placebo. Therefore, using a significance of 0.025 (to allow for two comparisons), with 90% power, we would need 137 participants per treatment group (total 411). Allowing for 20% loss to follow-up we aim to recruit 516 participants (172 per centre).

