### **9.4 Randomisation, blinding and unblinding**

Randomisations lists will be prepared by the study statistician. Each Site Pharmacy will be provided with two randomisation lists, one for patients not allergic to penicillin and one for those who are. These will be block randomised with randomly chosen balanced blocks of six or nine. As patients are recruited they are assigned the next vacant Participant Identification number (PID). The randomisation list will link each unique PID to a treatment group, denoted A, C or E for the non-penicillin allergic group; and B, D and F for the penicillin allergic group. The pharmacist will then select a treatment pack(s) for the relevant treatment arm based on a trial pack randomisation list. This is to ensure that trial pack identification numbers cannot be used to identify treatment allocation. The Trial Pack contains the prescribed medication as detailed in Section 11.3. The process is described in more detail in the Trial Pack Randomisation Protocol.

At the point when a research nurse arranges to visit a potential participant, they will inform their local Site Pharmacy who will begin preparing a Trial Pack based on the faxed prescription received from the clinician and the randomisation list.

Therefore, site pharmacists will not be blinded, but the research nurses will remain blinded at all times.

The research nurse will collect the Trial Pack(s) from the Site Pharmacy and transport the Trial Pack to the patient's home. The research nurse will only release Trial Pack(s) once informed consent has been obtained and a Consent Form signed. Participant randomisation will be considered to have occurred once a Consent Form has been signed and the Trial Pack opened. The Trial Pack number will then have been entered onto the participant's CRF. If consent is not obtained then the Trial Pack will be returned to the study pharmacy, logged and destroyed. Further details for IMP destruction will be provided to the research nurse and site pharmacies in a trial-specific IMP management standard operating protocol.

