## 15 Analysis

### 15.1 Main analysis

The primary analysis will be an intention to treat analysis comparing POEM scores at two-weeks in the treatment groups with active medicine with those in the placebo only group. We will do this using ANCOVA, controlling for baseline POEM score. This approach makes certain assumptions about the data, which will be tested prior to analysis. If the data do not fit with these assumptions then we will use a non-parametric approach. Further detail will be provided in the Statistical Analysis Plan.

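### Testing both active-versus-placebo comparisons at 0.025 would be valid, but Holm's procedure gives more power to show both effects at the same 5% family-wise error

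*Protocol*

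**What the plan says.** Section 14.4 of the protocol describes the primary analysis as two comparisons: "The main analysis will be a comparison of each active treatment with placebo". It draws the significance level from that, "using a significance of 0.025 (to allow for two comparisons"), and concludes that "with 90% power, we would need 137 participants per treatment group (total 411"). The effect behind this is set out as follows: "Assuming a clinically important difference of 3 on the POEM score and a common standard deviation of 7", from which "we estimate a meaningful effect size of 0.429".

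Section 15.1 describes the primary analysis as intention to treat, "comparing POEM scores at two-weeks in the treatment groups with active medicine with those in the placebo only group", by ANCOVA adjusted for baseline POEM. A non-parametric method is the fallback if the assumptions fail. Section 15.1 gives no test level and no multiplicity procedure, and leaves further detail to the SAP, which is not at hand.

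Section 9.4 sets equal allocation: "These will be block randomised with randomly chosen balanced blocks of six or nine".

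**The concern.** A reader who has only the protocol would test each primary comparison at 0.025, because no other rule is given for them. That is the Bonferroni rule. Holm's procedure tests the smaller p-value at 0.025 and, if that is rejected, the other at 0.05. It rejects everything Bonferroni rejects and sometimes more, and it has the same strong control of the family-wise error at 5%.

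The stake is the chance of settling both questions. The primary objective (section 5.1) covers oral and topical antibiotics alike, and the rationale (section 4.2) asks which route does more good. A trial that resolves one comparison and narrowly misses the other answers only part of that. The second step of Holm helps in exactly this situation.

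**Working it through.** **Inputs.** From section 14.4: difference 3, SD 7, level 0.025 per comparison, power 90%, loss to follow-up 20%. From section 9.4: equal allocation, so the two test statistics share the placebo arm and correlate at 0.5. Sidedness is not stated. Two-sided 0.025 reproduces the protocol's figure; one-sided 0.025 gives 115 per group and does not.

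**The plan's own figure.** With d = 3/7 = 0.429,

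n = 2(z₀.₉₈₇₅ + z₀.₉₀)²/d² = 2(2.241 + 1.282)²/0.429² ≈ 135.1, so 136 per group by the normal approximation.

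The t-test version gives 136.4, so 137. Loss to follow-up: 137/0.8 = 171.25, so 172 per group, and 3 × 172 = 516. The stated 137 and 516 both reproduce.

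**Power with 0.025 for each test.** The non-centrality is 0.4286 × √(137/2) = 3.547. Power per comparison is Φ(3.547 − 2.241) = Φ(1.306) = 90.4%. With correlation 0.5 and a 3-point effect in both arms, the bivariate normal gives 83.9% for rejecting both. At least one is rejected with probability 2 × 90.4 − 83.9 = 96.9%.

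**Power with Holm.** Holm adds a rejection only when one |z| exceeds 2.241 and the other lies between 1.960 and 2.241. With the full effect in both arms, that happens about 3.0% of the time for each comparison. Power per comparison therefore becomes 90.4 + 3.0 = 93.4%, and power for both becomes 83.9 + 2 × 3.0, which is 89.8% before rounding. The first step is unchanged, so the chance of at least one rejection stays at 96.9%.

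| 137 per group, SD 7, two-sided | 0.025 for each | Holm |
|---|---|---|
| Both arms 3 points: each comparison | 90.4% | 93.4% |
| Both arms 3 points: both shown | 83.9% | 89.8% |
| Both arms 3 points: at least one shown | 96.9% | 96.9% |
| One arm 3, other 1.5 points: the weaker arm | 32.0% | 42.1% |
| One arm 3 points, other none: the effective arm | 90.4% | 90.6% |
| No effect in either arm: any rejection | 4.6% | 4.6% |

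Step-down Dunnett uses the correlation of 0.5, with critical value 2.212 and then 1.960. It adds little to Holm: 93.5% per comparison and 89.9% for both when both arms work.

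**Effect of the planned ANCOVA.** The protocol gives no correlation between baseline and two-week POEM, so r is assumed here. The SD becomes 7√(1 − r²).

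- r = 0.3: SD 6.68. Power per comparison at 0.025 is 93.0%. Power for both goes from 88.0% to about 92.8% with Holm, a gain of about 5 points.
- r = 0.5: SD 6.06. Power per comparison at 0.025 is 96.8%. Power for both goes from 94.3% to 96.9%, a gain of about 3 points.

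**The case against.** The strongest reply is that the protocol does not fix Bonferroni as the test. The 0.025 stands in the sample-size section, Bonferroni is never named, and section 15.1 leaves detail to the SAP. Sizing at 0.025 is compatible with testing by Holm, and the SAP may already say so. This stands, and it is why the point is conditional on how the analysis is run. What remains is that section 14.4 derives 0.025 from the main analysis itself and offers no alternative.

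A second reply is that the gain depends on the scenario. That also stands. The gain is material when both antibiotics work to some degree and close to nothing when only one does. Sections 4.1.4 and 4.2 treat benefit from antibiotics as uncertain. In the half-effect case, 42% is still low power.

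A third reply is that single-step testing at 0.025 agrees with simple 97.5% confidence intervals, and Holm's second step need not. A sponsor may reasonably value that agreement. It is a real trade-off and belongs in the decision.

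Three stronger readings are tempting, and the documents support none of them.

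- A reader might infer that the sample size or the error control is wrong. Both are correct.
- A reader might take the 4.6% family-wise error as a defect that Holm repairs. Holm has the same 4.6% when neither arm works.
- A reader might infer that fewer children would do, since about 122 per group gives 90% power per comparison under Holm when both arms work. That fails if only one antibiotic works, so 0.025 remains the safe basis for sizing.

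**Conclusion.** The protocol contains no error on this point. If both primary tests are run at 0.025, the analysis is valid and sufficiently powered per comparison, but less efficient than it could be. The cost is about 6 points of power to show both effects and about 3 points per comparison, given 137 followed up per group, SD 7 and a true 3-point effect in both arms. For an arm with half that effect, the cost is about 10 points. It is about 0.2 points if only one antibiotic works, and nil for the chance of at least one rejection. A baseline correlation above zero reduces the both-arms figure, to about 5 points at an assumed 0.3 and about 3 at 0.5. This is an optional efficiency improvement, and it lapses if the SAP already names a step-down procedure.

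**What to change.** Keep 137 per group and 516 in total, sized at 0.025. State in section 15.1, or confirm in the SAP before unblinding, that the two primary comparisons are tested by Holm: the smaller p-value against 0.025 and, if that is rejected, the other against 0.05. Show the Holm-adjusted p-value beside the 97.5% confidence interval for each difference. Holm needs only the two p-values, so it also serves if the non-parametric fallback is used.

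The cost is one or two sentences, with no extra participants, data or change to the ANCOVA. The drawback is that a 97.5% interval may include zero for a comparison rejected at the second step. The report should say so in advance, so that the adjusted p-value and the interval are not read as contradicting each other.

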## 15 Analysis

### 15.1 Main analysis

The primary analysis will be an intention to treat analysis comparing POEM scores at two-weeks in the treatment groups with active medicine with those in the placebo only group. We will do this using ANCOVA, controlling for baseline POEM score. This approach makes certain assumptions about the data, which will be tested prior to analysis. If the data do not fit with these assumptions then we will use a non-parametric approach. Further detail will be provided in the Statistical Analysis Plan.

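### Section 15.1 lets assumption tests on the trial data replace the primary ANCOVA with an unnamed non-parametric method, and the stated model leaves out the randomisation strata

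*Protocol*

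**What the plan says.** Protocol section 15.1 sets an intention-to-treat comparison of two-week POEM between the active arms and placebo. On the model it says: "We will do this using ANCOVA, controlling for baseline POEM score". It continues: "This approach makes certain assumptions about the data, which will be tested prior to analysis". The consequence of a failed check is: "If the data do not fit with these assumptions then we will use a non-parametric approach". The paragraph closes with "Further detail will be provided in the Statistical Analysis Plan".

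On allocation, section 9.4 says: "Each Site Pharmacy will be provided with two randomisation lists, one for patients not allergic to penicillin and one for those who are". It adds: "These will be block randomised with randomly chosen balanced blocks of six or nine". Randomisation is therefore stratified by Site Pharmacy and penicillin allergy. Neither factor is in the model of section 15.1. Neither is in the further adjusted analysis of section 15.2, which uses age, sex and the baseline skin-swab findings for *S. aureus*.

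Section 14.4 sizes the trial on a mean difference: "Assuming a clinically important difference of 3 on the POEM score and a common standard deviation of 7", "using a significance of 0.025 (to allow for two comparisons), with 90% power". This gives 137 evaluable children per group, 411 in total, and 516 to be recruited.

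**The concern.** There are two parts, and the first matters more.

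**The switch.** Checking ANCOVA assumptions means looking at the outcome data, so the choice of headline analysis is made after the outcome has been seen. The protocol gives no test, no threshold and no named replacement. POEM takes whole-number values from 0 to 28, and scores pile up near the floor as children improve. A formal normality test on several hundred such scores can reject even though inference on the mean difference is sound. The rule may therefore fire when nothing is wrong. Some methods that fit the wording, such as a two-sample rank test, give neither a baseline-adjusted result nor a difference in POEM points. Such a result could not be read against the 3-point difference on which the trial is sized, or used in the economic analysis of section 15.4, which works with mean POEM scores.

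**The strata.** Stratified blocking balances the arms within pharmacy and allergy list. If those factors predict outcome and are left out of the model, the reported standard error does not reflect that balance and is somewhat too large.

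**Working it through.** **1. The plan's own figure.** Inputs from section 14.4: difference 3, SD 7, alpha 0.025, power 90%. Taken as two-sided, z = 2.241 and 1.282:

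n = 2 × (2.241 + 1.282)² × (7/3)² ≈ 135.1, so 136 per group. The exact noncentral-t version gives 137, with power 90.1%. Then 137/0.8 = 171.25, so 172 per group, and 3 × 172 = 516. The stated 137, 411 and 516 reproduce. The calculation is an unadjusted two-sample comparison and takes no credit for baseline POEM.

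**2. Power of the two analyses at 137 per group.** The correlation ρ between baseline and two-week POEM is not in the protocol; 0.3 to 0.6 is assumed.

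- ANCOVA uses residual SD = 7 × √(1 − ρ²). For ρ = 0.3 the SD is 6.68 and power 93.0%. For ρ = 0.5 the SD is 6.06 and power 96.8%. For ρ = 0.6 the SD is 5.60 and power 98.6%.
- A plain rank test without baseline has relative efficiency 3/π under normality. Effective n = 137 × 3/π ≈ 130.8, giving power 89.0% whatever ρ is. Reaching 90% would need 136 × π/3 ≈ 142.4, so 143 per group.

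A plain rank test would thus be about 1 point below planned power and 4 to 10 points below the specified ANCOVA.

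**3. Simulation of the switch.** Two arms of 137 were simulated with scores rounded and limited to 0-28. Assumed inputs were baseline mean 13, two-week placebo mean 10 and SD 7 before limiting. The assumed rule was a Shapiro-Wilk test on ANCOVA residuals at 5%, leading to a Mann-Whitney test if it rejects. There were 2,000 runs per setting, so the simulation standard error near 2.5% is √(0.025 × 0.975/2000) ≈ 0.35 points.

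| ρ | True difference | ANCOVA rejects | Rank test rejects | Switch fires | Two-stage rule rejects |
|---|---|---|---|---|---|
| 0.3 | 0 | 2.4% | 2.5% | 81.6% | 2.5% |
| 0.5 | 0 | 2.4% | 2.6% | 41.6% | 2.6% |
| 0.6 | 0 | 2.6% | 2.9% | 26.6% | 3.0% |
| 0.3 | 3 | 92.4% | 88.2% | 95.0% | 88.2% |
| 0.5 | 3 | 95.8% | 87.8% | 64.5% | 90.8% |
| 0.6 | 3 | 98.3% | 89.4% | 41.6% | 94.4% |

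ANCOVA holds its size on the bounded score. A separate simulation with ρ of 0.4 to 0.6 agreed: size was 2.3%-3.1% (simulation error about 0.4 points), and residual normality was rejected in 14%-99% of runs. How often the switch fires depends heavily on the settings, but under this rule it can fire often while ANCOVA is valid.

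**4. Omitted strata.** If the strata explain a share v of residual variance, the reported standard error is too large by the factor 1/√(1 − v). The shares are assumed.

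- v = 2%: 1/√0.98 = 1.010, or 1.0% too large.
- v = 5%: 1/√0.95 = 1.026, or 2.6% too large.
- v = 10%: 1/√0.90 = 1.054, or 5.4% too large.

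From the protocol's unadjusted base, true size falls from 2.5% to 2.4%, 2.2% and 1.8%. Power is 90.2%, 90.6% and 91.2% with strata omitted, against 90.6%, 91.5% and 93.0% with strata included. The loss is therefore 0.4, 0.9 and 1.8 points. With baseline adjustment (ρ = 0.5, three near-equal strata simulated), omitting against including gave 96.1% and 96.1% at v = 1%, 97.4% and 97.6% at 5%, and 98.1% and 98.7% at 10%. The loss there is under 1 point.

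**The case against.** The strongest reply has four parts.

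- **The text does not say rank test.** A reader might infer that the fallback is an unadjusted rank test. Section 15.1 says only that it is non-parametric. A rank ANCOVA would keep the adjustment, and a bootstrap of the ANCOVA coefficient would keep both the adjustment and the POEM-point estimate. Section 15.4 uses the same term for a bootstrap of mean cost differences; that concerns costs and does not settle the POEM fallback, but it shows a wider use of the word. This objection stands, so the power and estimate losses above are conditional.
- **Detail is left to the analysis plan.** The criterion, the named fallback and any design covariates may be settled there, and their absence from a protocol is not in itself a fault. This stands in part. The rule that ANCOVA is replaced when checks fail is stated in the protocol itself, and further detail would refine that commitment rather than remove it. For the strata it carries more weight, because the short model statement does not rule out extra terms.
- **Power is not below plan in any serious way.** A reader might infer an underpowered trial. Even a plain rank test gives about 89% against a planned 90%. The larger gap is measured against ANCOVA and rests on a correlation the protocol does not give.
- **Error control is not shown to fail.** A reader might expect a data-driven choice of test to inflate type I error. The two-stage rule rejected in 2.5%-3.0% of null runs, close to nominal given the simulation error, and omitting strata makes the test slightly conservative.

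**Conclusion.** The point holds as a weakness in how the primary analysis is fixed. Section 15.1 allows a check on the outcome data to replace a method that remains valid for this score and sample size, and does not say with what. If the replacement were a plain rank test, the trial would lose its baseline-adjusted mean difference in POEM points. Power would be about 89%, against 93.0%-98.6% for ANCOVA. That contrast assumes ρ of 0.3 to 0.6 and a difference of 3 with SD 7.

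The omitted strata are a smaller matter. Standard errors are about 1% to 5% too large if strata explain 2% to 10% of residual variance. The power cost is under 1 point with baseline adjustment and at most 1.8 points from the unadjusted base.

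The protocol does not support calling this a must-fix fault: size stays near nominal and power stays close to or above plan. It is a cheap improvement to make before the data are unblinded.

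**What to change.** State in section 15.1, and carry into the analysis plan, that the primary analysis is an ANCOVA of week-2 POEM on treatment arm, baseline POEM, Site Pharmacy and penicillin-allergy list (main effects), reported whatever the assumption checks show. Add that, if the checks raise concern, the same estimate is kept with heteroscedasticity-robust or bootstrap confidence intervals, and that any rank-based analysis is a sensitivity analysis only.

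The cost is two sentences, no new data and a few degrees of freedom. If there were three Site Pharmacies (an assumption, one for each of the regions supplied in section 11.3), the added terms would use 2 + 1 = 3. With 411 evaluable children, a three-arm model would go from 411 − 4 = 407 residual degrees of freedom to 404.

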### 15.2 Secondary analyses

We will also:

- Create a binary success/failure score based on what is deemed a clinically important change in POEM score (both absolute and percentage changes will be investigated and an appropriate method chosen), which will be analysed using logistic regression, controlling for important patient characteristics.
- Conduct a Complier Average Causal Effect (CACE) analysis (this approach is recommended over a per-protocol analysis <http://www.hta.ac.uk/fullmono/mon1143.pdf>) and an analysis adjusted for age, sex, and presence and resistance characteristics of *S. aureus* on skin swab at baseline. Differences in EASI scores IDQoL/CDLQI scores and DFI scores will be assessed using the same approach.

- Explore the rate of recovery using data from the daily symptom diaries. We will compare time to recovery using survival analysis based on the carers' reported 'day recovered' and compare the rate of change of a total daily symptom score in the three groups.
- Describe parent/carer(s)' preference for treatment (cream or oral suspension). Differences in preference between the three groups will be compared using a chi-squared test.
- Describe prevalence of specified organisms and resistance among those organisms (as percentages with 95% confidence intervals). The research team will describe the prevalence of *S. aureus* isolates from swabs of infected eczema, and methicillin and fusidic acid resistance amongst those isolates, in each group at baseline, 2 weeks, 3 months, and 12 months. In addition to presenting crude proportions, in the 3 and 12-month analyses the research team will adjust for subsequent courses of antibiotics. Furthermore, in order to describe the effect of each treatment on the development of resistant organisms, the research team will describe the prevalence of methicillin and fusidic acid resistance in *S. aureus* isolates from the anterior nares, and the prevalence of resistance to oxacillin and erythromycin in *S. pneumoniae* isolates from the oral cavity, at the same time points.
- An exploratory analysis will investigate the effectiveness of erythromycin compared with flucloxacillin.

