### **13.5 Collection of swab samples**

Swabs will be collected at baseline, 2 weeks, 3 months, and 12 months. Swabs will be taken from suspected infected eczema to identify *S. aureus* or Group A Streptococcus infection, nasal swabs for *S. aureus* carriage, and oral swabs to identify any change in frequency of penicillin or macrolide resistance in Group A Streptococcus commensal flora. Research nurses will take the baseline and 2-week swabs and parent/carer(s) will be asked to take the swabs at 3 months and 12 months.

The research nurses will provide parent/carer(s) with training in taking swabs during the 2-week visit. Parent/carer(s) will be sent a postal reminder and packaging at 3 months and 12 months. Parent/carer(s) will be provided with swabs, a postage-paid packaging for returning the swabs, and written instructions on collecting them, prior to these two collection points.

The research nurse or delegated member of the research team will contact the parent/carer(s) who have not returned the swabs by telephone in order to remind them to do so. In addition, if the parent/carer is contacted by the research team

about the questionnaire or contacts the research team for any other reason, the researcher will again encourage collection of the specimens. Collection of nasal swabs is likely to be the most difficult for the carers. In addition to providing training, we will be using short swabs that cannot be inserted too far into the nose. Such an approach has been shown to be feasible in other studies , even when this involves deeper swabbing (from the turbinates) .

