### **13.6 Microbiology processing**

The Specialist Antimicrobial Chemotherapy Unit (SACU) in Cardiff will receive the samples and log the date and time of receipt of the three different samples alongside the Patient ID and Date of Birth.

Nasal swabs will be cultured and any *S. aureus* will be confirmed and semi quantitative counts determined along with antimicrobial susceptibilities.

Infected eczema swabs will be cultured and *S. aureus* and Streptococci identification/grouping will be confirmed and semi quantitative counts determined along with antimicrobial susceptibilities.

Oropharyngeal swabs will be cultured and any streptococcus species found on non-selective and antimicrobial selective media will be confirmed and quantitative counts determined.

All isolates will be stored at -80°C storage. SACU will enter data into their own database which will be transferred securely to the Data Manager every month and merged with the CREAM database. To ensure all samples are returned at their required time points, SACU will inform the Trial Manager or Data Manager within 24 hours of receiving samples. The Data Manager will monitor the return of swabs and follow up with parent/carer(s) if any swabs are missing. Further details of the microbiology process, will be defined in a study-specific microbiology manual.

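### The oral-swab resistance outcome names different organisms in sections 13.5 and 15.2, and resistance among isolates is not the per-child measure that the comparative objective needs

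*Protocol*

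**What the plan says.** On the oral swab, three sections of the protocol describe the target:

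- Section 13.5 (collection) plans "oral swabs to identify any change in frequency of penicillin or macrolide resistance in Group A Streptococcus commensal flora".
- Section 13.6 (laboratory) says that "any streptococcus species found on non-selective and antimicrobial selective media will be confirmed and quantitative counts determined". For the nasal and eczema swabs the same section lists antimicrobial susceptibilities. For the oropharyngeal swab it does not. Further detail is left to a microbiology manual.
- Section 15.2 (analysis) plans to report "the prevalence of resistance to oxacillin and erythromycin in" *S. pneumoniae* isolates from the mouth.

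On the measure of resistance, section 15.2 opens with a general plan to give the prevalence of the organisms and the resistance among them, as percentages with 95% confidence intervals. For skin swabs it specifies the prevalence of *S. aureus* isolates and "methicillin and fusidic acid resistance amongst those isolates, in each group at baseline, 2 weeks, 3 months, and 12 months". It then introduces the nasal and oral isolate figures as a way to describe what each treatment does to the development of resistance.

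On later antibiotics, crude proportions are to be presented, and in addition "in the 3 and 12-month analyses the research team will adjust for subsequent courses of antibiotics".

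Section 5.2 holds two relevant objectives. One compares oral and topical treatment on, among other things, how common carriage of or infection with resistant organisms is. The other is descriptive: the long-term prevalence of resistant isolates in each of the three groups.

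**The concern.** Group A Streptococcus and *S. pneumoniae* are different organisms, so sections 13.5 and 15.2 cannot both define the oral outcome. Unless this is settled before the data are seen, the organism could be chosen after results are known, and the laboratory summary does not show which resistance result the analysis will receive.

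The second problem is the denominator. A percentage among isolates is computed only in children from whom the organism was grown. An antibiotic that removes sensitive strains shrinks that denominator, and the percentage rises even if no additional child carries a resistant strain. The arms are then compared in groups selected by the treatment itself. That does not suit a statement about treatment effect.

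Third, antibiotic courses after randomisation may themselves be changed by the allocated treatment. Adjusting for them gives a different quantity from the total effect of allocation, and the protocol does not say which analysis leads.

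Resistance is part of the trial's rationale in section 4.2, and it is the reason for swabbing children over 12 months.

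**Working it through.** **1. The oral outcome, side by side**

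| Section | Organism | Resistance |
|---|---|---|
| 13.5 | Group A Streptococcus | penicillin or macrolide |
| 13.6 | any streptococcus species | growth on antimicrobial-selective media (drugs not named); no susceptibility test listed |
| 15.2 | *S. pneumoniae* | oxacillin and erythromycin |

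The drug pairs might be reconciled as class and member; the organisms in 13.5 and 15.2 cannot. The wording in 13.6 is broad enough to contain both, so it contradicts neither, but it does not settle which is meant.

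**2. The plan's own figure**

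No figure is stated for resistance. The only number used below is 137 children per group, from section 14.4. It reproduces: a difference of 3, SD 7, two-sided significance 0.025 and 90% power give 136 per group by the normal approximation and 136.4 by the t-test, rounded up to 137. Then 137 / 0.8 = 171.25, rounded up to 172, and 3 × 172 = 516.

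**3. Among isolates against per child**

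All rates here are assumptions, because the protocol gives none. In the placebo arm, 70% of children carry *S. aureus* and 7% of all children carry a resistant strain, which leaves 63% with a sensitive strain. The active drug clears a fraction c of sensitive strains and no resistant ones.

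- Carriage on active drug = 0.63 × (1 − c) + 0.07
- Resistance among isolates = 0.07 / carriage
- Resistant carriage per child = 0.07 in every case

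| | Carriage | Isolates out of 137 | Resistant among isolates | Resistant per child |
|---|---|---|---|---|
| Placebo | 0.70 | 96 | 0.07 / 0.70 = 10.0% | 7.0% |
| c = 25% | 0.5425 | 74 | 0.07 / 0.5425 = 12.9% | 7.0% |
| c = 50% | 0.385 | 53 | 0.07 / 0.385 = 18.2% | 7.0% |
| c = 75% | 0.2275 | 31 | 0.07 / 0.2275 = 30.8% | 7.0% |

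The comparison among isolates shows a rise of 2.9 to 20.8 percentage points where resistant carriage does not change.

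**4. Adjusting for later antibiotics**

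A simulation of 2 million children had no direct treatment effect on resistance, a base resistance of 5%, and 8 points added by a later antibiotic course.

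- Later use 40% on placebo, 23% on active: expected total difference 0.08 × (0.23 − 0.40) = −1.4 points; simulated crude −1.4, adjusted −0.04.
- Later use 40% on placebo, 50% on active: crude +0.8, adjusted +0.03.
- Later use 40% in both: crude and adjusted both about +0.1, which is simulation noise.
- With an unmeasured severity factor raising both later use and resistance (later use 42% and 27%): crude −1.2, adjusted +0.1.

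Adjustment removes the part of the effect that runs through later antibiotics; the crude comparison keeps it. If treatment does not alter later use, the two agree.

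**The case against.** Several points on the other side are sound.

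- Crude proportions are already planned alongside the adjusted ones, so the adjustment replaces nothing. The adjustment sentence follows the skin-swab text, and whether it reaches the nasal and oral swabs is unclear. This part of the point therefore concerns only which analysis is labelled as main.
- Organism prevalence is planned too. Multiplying it by resistance among isolates recovers the per-child figure (0.385 × 0.182 = 0.07). That holds for the point estimate. However, prevalence by group is spelled out only for eczema swabs, and nowhere is the per-child proportion, or an interval for its difference between arms, made the comparison.
- The descriptive objective in section 5.2 asks for resistant isolates, and the isolate denominator answers it as written.
- Growth on selective media is itself a reading of resistance, isolates are stored, and a microbiology manual exists. The missing susceptibility entry in section 13.6 does not show that no testing is planned.
- Swabbed children are also a group formed after randomisation. Skin swabs need infected eczema to swab, and the 3- and 12-month swabs depend on parents sending them back. A per-child denominator removes the selection on having an isolate, but not this one.

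A reader might infer that three different organisms are named, or that the laboratory work cannot support the outcome. The documents support neither: the contradiction is between two sections, and the laboratory detail is unresolved rather than shown to be wrong.

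**Conclusion.** The oral-swab outcome is contradictory between sections 13.5 and 15.2, and section 13.6 does not resolve it. That follows from the text and needs no assumption.

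The among-isolates measure does not directly answer the comparative objective. In the illustration it moves from 10.0% to between 12.9% and 30.8% while resistant carriage stays at 7.0%. The size rests entirely on the assumed carriage and clearance rates; the direction rests on treatment clearing sensitive strains more readily than resistant ones.

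It would be tempting to conclude that the resistance objective cannot be answered without bias. The documents do not support that: crude proportions and organism prevalence are both planned, the per-child estimate can be derived from them, and the descriptive objective can be met as it stands. Nor is it shown that adjusting for later antibiotics would reverse the direction of a finding. On the assumptions tried, it brought the estimate to about zero. The adjustment becomes a problem only if it is read as the main result.

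**What to change.** 1. The sponsor and the laboratory name one oral organism and drug set that the laboratory method supports, and use it in sections 13.5, 13.6 and 15.2. Section 13.6 should state how resistance is read from this swab.
2. For the comparative objective, report the proportion of swabbed children in each randomised arm who carry a resistant organism, with risk difference and 95% CI, counting a child with no isolate as not carrying one. For skin swabs, state how a child with no infected eczema left to swab is counted.
3. Report swab return by arm at each time point, above all at 3 and 12 months.
4. Keep resistance among isolates as a descriptive table.
5. Label the crude comparison by randomised arm as the main one, and the analysis adjusted for later antibiotics as supportive. State which swab sites the adjusted analysis covers.

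The cost is a wording change in three sections and a re-tabulation of data that are already to be collected. Unless the organism and drug set agreed under item 1 calls for testing not already planned, no extra laboratory work is implied.
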